## ***Data Collection***

We evaluated quantitative data 12 months before the first facilitation visit (pre-intervention) to six-months after the last facilitation visit (post-intervention). Pre-intervention interviews and survey data were collected between November 2020 and July 2021. We delayed the intervention start for Intervention Clinic 2 (IC2) to allow them to prioritize their COVID response, adjusting data collection for IC2 and its matched control clinic 2 (CC2). Monthly check-in calls with ICs started in the month following the first intervention visit (December and June, respectively) and continued for the duration of the intervention. Post-intervention survey and interviews were conducted between March and June 2022 for IC1 and between June and July 2022 for IC2.

Survey data. We conducted two surveys. One was completed by the office manager or clinical leader from each clinic (N=4). This survey collected clinic demographic data and 14 items from the Change Process Capability Questionnaire (CPCQ), which was modified to assess a medical groups use of quality improvement strategies aligned with improve type 2 diabetes care.

Demographic data were collected once, pre-intervention. The CPCQ was completed pre- and post-intervention (see Appendix 2). ICs and CCs completed this survey with a 100% response rate. The second survey assessed the feasibility, acceptability and appropriateness of INTEGRATE-D using three psychometrically assessed measures developed by Weiner et al. This survey was distributed to clinical team members exposed to the intervention (N=17) after the intervention ended, with an 82% response rate. Surveys were conducted using REDCap.

EHR data. EHR data were abstracted through a combination of manual and automated reporting, both of which followed a protocol. Research staff assisted clinic staff with creating a list of patients with type 2 diabetes seen in the clinic at least once in the 15 months prior to the

intervention start and once during the intervention. Using a random number table, we selected 50 patients from this list. The same procedure was used to generate a list of 30 patients who had depression symptoms (PHQ-9 >9) or for elevated DD using the 2-question or long screener. Of those patients, chart auditors further assessed behavioral health outcome measures. The A1C measure was assessed for these two groups. Staff conducting chart audits were trained to determine which individuals to include in numerators and denominators, which clinical data to include and appropriate parameters to record.

**Interviews.** Experienced qualitative researchers conducted semi-structured interviews (see Online Appendix) and monthly checks with clinics. Pre-intervention clinic member interviews (n=19) explored experiences with delivering psychosocial care to patients with type 2 diabetes. Post-intervention interviews (N=5) and one email interaction complemented post-intervention surveys. Interviews were conducted with those exposed to the intervention and explored their experience with the intervention and the changes they implemented. Monthly phone check-ins were conducted with one person from each IC to monitor progress; notes were prepared from these conversations. Patients from the two ICs (N=5) were interviewed to explore their experiences of integrated psychosocial and diabetes care and how it may have changed.

**Practice facilitator data.** The facilitator completed notes following each session documenting what they worked on with the clinic, resources shared, progress, planned quality improvement cycles, successes and challenges. Monthly study team check-ins with the facilitator complemented these notes and allowed for monitoring progress and fidelity. Notes were developed to document these conversations.

Clinic member and patient interviews generally lasted 30-45 minutes, were conducted via telephone or web platform, audio-recorded with permission, professionally transcribed, and reviewed for accuracy. Qualitative data were de-identified and organized into Atlas.ti7 for management and analysis.

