**Table 1. Intervention Components, Description, Frequency and Timeline**

Intervention Component	Who Provided Support	Description	Frequency and timeline
Expert Training	Physician, BHC, and expert in implementing DD	Education for clinical teams in ADA recommendations and self-management support materials  1.Psychosocial care, type 2 diabetes and DD training for all clinical roles delivered by a physician and DD expert 2.BHC training about the role of the BHC in caring for patient with type 2 diabetes delivered by a clinical	IC1 received these remotely March and May 2021  IC2 was given a recording of these trainings. We do not

		psychologist with expertise in integrated behavioral health and primary care	know if these were reviewed by IC2.
Facilitation	Practice Facilitator	
Customized remote once-a-month meetings with an experienced practice facilitator using Bodenheimer's Building Blocks framework utilizing Plan Do Study Act (PDSA) cycles. Meeting topics were tailored to the clinic's experience and aligned with ADA recommendations and included:
 
 
• Patient education materials for BH and self-management support
 
• Implementation of systematic screenings for DD, depression, anxiety
 
• Identifying changes in roles/responsibilities, new processes/workflows for screening and treatment
 
• Identify cross-functional practice team, train team in QI
 
• Proactive outreach to patients regarding DMII, self-management status, community and family needs
 
• Pre-visit planning and huddling, scheduling BHC visits with warm handoffs
 
	IC1: December 2020-February 2022 IC2: June 2021-May 2022

IC=Intervention Clinic; BHC=Behavioral Health Clinician; DD=Diabetes Distress; QI=Quality Improvement; DMII=Type 2 Diabetes Mellitus; ADA=American Diabetes Association

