### ***Data Sources and Measures***

Table 2 shows the data sources and measures used to assess the feasibility and effect of INTEGRATE-D.

Table 2. Study measures, variables and data sources

Assess the feasibility, appropriateness and acceptability of INTEGRATE-D		
VARIABLE/ DEFINITION	DATA SOURCE	DATA COLLECTION / ANALYSIS
Acceptability – extent to which intervention is agreeable, palatable, satisfactory	Assessed via survey  and semi-structured interview. Survey had four questions per variable. See Online Appendix for items.	Collected from clinic members exposed to the intervention (intervention clinics) at the end of the intervention.
Appropriateness – extent to which intervention fits and is compatible for addressing issue or problem		Descriptive analysis for ICs only. Survey scores, which ranged from 1 (strongly disagree) to 5 (strongly agree) for each clinic member response were averaged at the clinic-level.
Feasibility – extent to which an intervention can be successfully used or carried out		
Compare changes in use of quality-improving strategies		
Clinics' ability to implement quality improving strategies related integrated type 2 diabetes care	Assessed via survey using 14 items from the Change Process Capability Questionnaire (CPCQ).  See Online Appendix for items.	One person at intervention and control clinics completed the survey at the same time, pre- and post-intervention.  Survey scores, which ranged from -2 (strongly disagree) to +2 (strongly agree), were summed for each clinic with possible sums ranging from -28 to +28. Average aggregate scores were compared between intervention vs. control clinics
Compare changes in process of care screening rates		
A1C screening – binary variable indicating whether the patient was screened at least once during the period	Electronic Health Record (EHR) data abstracted through manual and automated methods	Operationalized at the patient level for pre- and post-intervention periods, means aggregated at the clinic-level for intervention and control clinics. Pre-intervention defined as the time during the 12 months before the intervention; post-intervention defined as any time during the 12 months following the start of the intervention.
Cholesterol screening - binary variable indicating whether the patient was screened at least once during the period		

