Nephropathy screening - binary variable indicating whether the patient was screened at least once during the period		
Psychosocial screenings – binary variables indicating whether the patient was screened at least once during the period for depression (PHQ-2 and/or PHQ-9) and / or for diabetes distress (DD) 		
Compare changes in clinical outcomes (PHQ-9 scores and A1C levels)		
Behavioral health – change in symptoms (PHQ-9) for patients with depression symptoms (PHQ-9>9); data abstracted through manual and automated methods	Operationalized at the patient level for pre- and post-intervention periods, means aggregated for intervention and control clinics; pre-intervention defined as score closest to the intervention start date; post-intervention defined as score closest to the intervention end date.	
Diabetes Management – change in A1C for patients diagnosed with type 2 diabetes		
Confounding Variables - Patient socio-demographics, comorbidity, insurance, and utilization		
Age, gender, language preference, race/ethnicity, income/federal poverty level, insurance type, physical, mental/behavioral health comorbidity, healthcare utilization	EHR data abstracted through manual and automated methods	Operationalized at the patient level

 Diabetes distress (DD) screening was implemented by intervention clinics; clinics did not screen for this pre-intervention

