### ***Analysis***

Feasibility, acceptability and appropriateness of INTEGRATE-D were assessed post-intervention among ICs. For the other quantitative variables, we compared differences in values pre- and post-intervention among ICs and CCs. For the CPCQ as well as for feasibility, acceptability and appropriateness, we performed clinic-level analyses. For process-of-care measures, we performed patient-level analyses, with results summarized by clinic. When testing the effect of INTEGRATE-D on these outcomes, the independent variables were exposure to the intervention (whether the patient was associated with a clinic randomized to the intervention) and time period where baseline represented the closest measure available for the patient before the start of the intervention and follow-up represented the closest measure after the end of intervention.

To assess the effect of the intervention on A1C and PHQ-9 outcomes, we compared ICs and CCs performing a patient-level analysis using linear mixed effects models. We modeled the outcome of interest as a function of the indicator for period (post vs. pre), indicator for intervention arm (IC vs. CC), and the interaction between period and intervention, using random effects to account for repeated measures within the same patient over time. We adjusted for potential confounding using a range of patient-level characteristics (see Table 2). Statistical tests were two-side ( $\alpha=0.05$ ) and performed in R (version 4.2.0).

Qualitative researchers with expertise in primary care, integrated care and implementation science conducted analyses. We used a group process to analyze qualitative data, tagging text to assign codes that were aligned with emerging patterns/findings. When codes were clearly defined (i.e., we had a codebook) and used consistently among the team, we transitioned to individual data analysis. The team continued to meet to review work and discuss emerging findings. Tagged data was analyzed a second time to examine the similarities and differences across the two ICs. Qualitative findings were summarized and connected with quantitative findings to explain the study results.

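### Two clinic pairs on calendar schedules up to six months apart share one period effect, with no pair or pair-by-period term in the model

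*SAP*

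**What the plan says.** The SAP section Data Collection records that "We delayed the intervention start for Intervention Clinic 2 (IC2) to allow them to prioritize their COVID response", and that this meant "adjusting data collection for IC2 and its matched control clinic 2 (CC2"). By implication IC1 is paired with CC1, although the SAP does not say so or describe how pairs were formed.

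SAP Table 1 gives the facilitation dates: "IC1: December 2020-February 2022 IC2: June 2021-May 2022".

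SAP Table 2 sets the observation windows relative to each clinic's own dates:

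- Process measures: pre is "defined as the time during the 12 months before the intervention"; post is "defined as any time during the 12 months following the start of the intervention".
- A1C and PHQ-9: baseline is "defined as score closest to the intervention start date"; follow-up is "defined as score closest to the intervention end date".

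The SAP section Analysis models A1C and PHQ-9 with an "indicator for period (post vs. pre), indicator for intervention arm (IC vs. CC), and the interaction between period and intervention", plus patient random effects and patient-level covariates. For process measures it names exposure and time period as the independent variables. Protocol section 8 (Hypotheses 2 and 3) gives the same three fixed effects for its screening example and adds a random intercept for practice. Neither document has a pair, calendar-time or pair-by-period term.

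**The concern.** Pre and post are different stretches of calendar time in the two pairs, in a period that the SAP itself describes as disrupted by COVID-19. A single period coefficient assumes that the secular change from pre to post is the same for both. If it is not, the period-by-arm interaction is clean only when both arms contain the two pairs in the same proportion. If the proportions differ, part of the difference between the pairs' secular trends is read as an intervention effect.

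The analyses exposed to this are those of A1C and PHQ-9 scores, because patients can drop out of them:

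- The PHQ-9 outcome is restricted to patients with PHQ-9>9. The 30-patient list also admits patients who have elevated diabetes distress only.
- The footnote to SAP Table 2 says that distress screening was introduced by the intervention clinics and was not done beforehand. Distress-only patients may therefore be found mainly in that arm.
- If the two intervention clinics lost such patients equally, the pair mix would not change. Uptake may differ, however: IC1 had live training, while IC2 had recordings that may not have been reviewed (SAP Table 1).
- Missing A1C or PHQ-9 follow-up values can shift the mix in the same way.

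**Working it through.** The documents state no figure on this point, so there is none to reproduce.

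**1. Calendar windows** (dates from SAP Table 1, window rules from SAP Table 2)

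| | Pair 1 | Pair 2 | Gap |
|---|---|---|---|
| Process pre window | Dec 2019–Nov 2020 | Jun 2020–May 2021 | 6 months |
| Process post window | Dec 2020–Nov 2021 | Jun 2021–May 2022 | 6 months |
| A1C/PHQ-9 baseline anchor (start) | Dec 2020 | Jun 2021 | 6 months |
| A1C/PHQ-9 follow-up anchor (end) | Feb 2022 | May 2022 | 3 months |
| Facilitation length | 15 months | 12 months | 3 months |

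For process measures, December 2020 to May 2021 counts as post in pair 1 and as pre in pair 2.

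**2. Bias formula.** Let g1 and g2 be the secular pre-to-post changes in the two pairs, with no intervention effect. Let w_I and w_C be pair 1's share of analysed patients in the intervention and control arms. The mean change in an arm is w·g1 + (1 − w)·g2, so the interaction estimates

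[w_I·g1 + (1 − w_I)·g2] − [w_C·g1 + (1 − w_C)·g2] = (w_I − w_C)(g1 − g2).

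This is for patients with both values and a linear outcome.

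**3. Share differences.** The first row is the planned sample (80 per practice in protocol section 5; 50 plus 30 in the SAP). The other counts are assumptions.

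| IC1, IC2 / CC1, CC2 | w_I | w_C | Bias as share of \|g1 − g2\| |
|---|---|---|---|
| 80, 80 / 80, 80 | 0.500 | 0.500 | 0 |
| 80, 60 / 60, 80 | 0.571 | 0.429 | 14% |
| 15, 30 / 30, 30 | 0.333 | 0.500 | 17% |
| 30, 15 / 15, 30 | 0.667 | 0.333 | 33% |
| 30, 10 / 20, 30 | 0.750 | 0.400 | 35% |

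**4. Check by simulation.** Patient change scores, 4,000 runs per scenario, no true effect. Assumed: SD of change 1.2 outcome units, no clinic variation unless stated. On change scores, a pair term is the same as pair-by-period.

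- 80 per clinic: bias 0 with or without the term. The standard error falls from 0.137 to 0.134 when the pairs differ by 0.5 units, and from 0.145 to 0.134 when they differ by 1.0.
- 80, 40 / 40, 80 with a 0.5-unit difference: the bias is 0.167 in absolute size without the term and about 0 with it. Type I error falls from 18.6% to 5.5%.
- Same counts with no difference between pairs: the term is unnecessary, and the standard error rises from 0.155 to 0.164, about 6%.
- 80 per clinic, 0.5-unit difference, clinic SD of change 0.2: type I error is about 27% without the term and 28% with it. The pair term does nothing for clinic-level variation.

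**5. Clinic-level test.** With two pairs, a paired test has 1 degree of freedom (critical t 12.71), against 2 unpaired (4.30). The smallest two-sided permutation p-value is 2/2² = 0.50 paired and 2/6 = 0.33 unpaired.

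**The case against.** The strongest reply is that the design already protects the estimate. Each arm holds one clinic from each pair and the chart samples are equal by design, so the pair trends cancel. For the process measures this largely stands: the outcomes are binary, and a sampled patient who was not screened counts as a no rather than dropping out. It is weaker for A1C and PHQ-9 scores, where the analysed numbers depend on who qualifies and who has a value.

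The A1C and PHQ-9 follow-up anchors are only three months apart, so the schedules are closer for those outcomes than the six-month figure suggests. That also stands, although the unequal interval from start to end (15 against 12 months) remains.

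Matching is mentioned once and not defined, and the documents do not say that the shared dates were meant to remove time trends. That purpose is an inference, and the point does not depend on it. Process results are summarised by clinic, so within-pair contrasts can be read there. The protocol also concedes that the design cannot establish effectiveness conclusively.

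Two stronger readings are tempting and should be resisted:

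- **Screening rates biased by several percentage points.** A 60/40 against 40/60 mix with secular gaps of 5 to 15 points gives 0.20 × 5 = 1 to 0.20 × 15 = 3 points. But the screening measures are where the mix is best protected, and the documents give neither the mix nor the gap.
- **Ignoring pairs badly inflates a clinic-level standard error.** The A1C and PHQ-9 tests are patient-level, and the planned clinic-level comparisons are descriptive. A formal paired test would also pay heavily in degrees of freedom.

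**Conclusion.** The omission is real, and its consequence is conditional. With equal analysed numbers per clinic there is no bias from this source and only a small loss of precision. With numbers that differ across pairs and arms, the interaction is biased by the difference in pair-1 share times the difference in secular change: 17% of that difference when one intervention clinic contributes half as many patients as each of the other three, and 14% to 35% over the unbalanced mixes tried. Imbalance is plausible for the PHQ-9>9 subset and for patients without A1C or PHQ-9 follow-up, but it is not shown. The documents report neither analysed counts per clinic nor secular changes, so no absolute size can be given. A reader might infer that the trial's estimates are in fact biased; the documents do not support that. The point also rests on IC1 and CC1 forming the other pair, which the SAP implies but does not state. The absence of a clinic-level effect from the SAP model is a separate issue that pair terms do not cure.

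**What to change.** Label: cheap improvement.

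- Add pair and pair-by-period as fixed effects to the patient-level models.
- Report the number of patients analysed per clinic and period for each outcome, so that readers can see whether the pair mix differs between arms.
- Show the IC1–CC1 and IC2–CC2 differences in change side by side, descriptively, without a formal paired clinic-level test, which would have 1 degree of freedom.
- State how the pairs were formed and confirm that CC1 was observed on IC1's dates.

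Cost: two model terms, slightly less simple reporting and no new data. If the mix is unequal but the secular trends agree, the standard error rises a little (about 6% in the unbalanced case above). If the mix is equal, the estimates should barely move, and the table of counts will show why.

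### The PHQ-9 arm comparison admits patients on an undated qualifying score, so entry can depend on screening that the intervention itself promoted

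*SAP*

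**What the plan says.** The SAP (Data Collection, EHR data) describes two chart samples. Fifty patients are drawn with random numbers from all eligible patients with type 2 diabetes. A further sample, apparently drawn the same way, is "a list of 30 patients who had depression symptoms (PHQ-9 >9) or for elevated DD using the 2-question or long screener". It continues: "Of those patients, chart auditors further assessed behavioral health outcome measures". A1C is assessed in both groups. The only dated entry conditions are a visit in the 15 months before the start and a visit during the intervention. Neither dates the qualifying score.

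Two other places bear on who can qualify and when:
- SAP Table 1 lists among the facilitation topics "Implementation of systematic screenings for DD, depression, anxiety".
- The footnote to SAP Table 2 says "Diabetes distress (DD) screening was implemented by intervention clinics; clinics did not screen for this pre-intervention".

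Table 2 defines the behavioral health outcome as "change in symptoms (PHQ-9) for patients with depression symptoms (PHQ-9>9", also undated, with the pre-intervention value "defined as score closest to the intervention start date". The Analysis section fits a linear mixed model with period, arm, their interaction, patient random effects and patient covariates, tested two-sided at 0.05. Its own description of baseline is the nearest measure before the start, although that sentence directly follows the process-of-care measures.

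Protocol section 5.i describes 80 randomly selected charts per practice and says that random sampling makes the results generalise to eligible patients.

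**The concern.** The intervention aimed to increase screening. If a score found by that screening can admit a patient to the outcome sample, the sample is selected on a post-randomisation event that differs by arm. The distress route shows that this is not hypothetical wording: no clinic screened for distress beforehand, so any entry by distress must rest on a score taken after the start. The list rule as written therefore accepts post-start scores, and nothing limits the PHQ-9 route to pre-start ones.

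Patients chosen for a high pre-start score tend to fall by regression to the mean. Patients who qualify only later do not show that fall, and they rise if the qualifying score is the follow-up itself. If the mix of the two differs between arms, the period-by-arm term moves with no treatment effect. None of the model's terms records how or when a patient entered.

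Two wordings also need reconciling. Data Collection appears to assess all 30 symptomatic patients, while Table 2 limits the PHQ-9 outcome to scores above 9, which would remove patients who entered by distress alone. Table 2's baseline is not explicitly restricted to scores before the start.

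**Working it through.** **Counts.** 50 + 30 = 80 per clinic and 4 × 80 = 320, matching protocol section 5.i. That the 50 and 30 are per clinic is inferred from this match. The PHQ-9 comparison then has at most 2 × 30 = 60 patients per arm. The symptomatic share of the A1C charts is 30/80 = 37.5%.

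**Assumed inputs for PHQ-9 (none in the documents).** Scores bounded 0 to 27 (beta-binomial), mean 7, SD 6, about 30% above 9, pre-post correlation ρ of 0.4, 0.6 or 0.8, no true effect, clustering ignored. Means come from simulating 2 million patients. All control patients qualify pre-start. An extra 10 percentage points of intervention patients qualify only after the start, with an analysed pre-start score of 9 or less. The false difference is 0.10 × (mean change in late qualifiers − mean change in pre-start qualifiers). Positive means that the intervention arm looks worse.

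| | ρ = 0.4 | ρ = 0.6 | ρ = 0.8 |
|---|---|---|---|
| Change, pre-start score above 9 | −4.79 | −3.26 | −1.66 |
| (a) Change, qualifies on the analysed follow-up | +9.29 | +7.92 | +5.90 |
| (b) Change, qualifies on a separate score during the intervention | +3.56 | +3.30 | +2.63 |
| False difference (a) | +1.41 | +1.12 | +0.76 |
| False difference (b) | +0.83 | +0.66 | +0.43 |

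Example for (a) at ρ = 0.6: 0.10 × (7.92 + 3.26) = 1.12.

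The standard error with 60 per arm is 1.22, 1.08 and 0.83. Allowing for the mixture, the bias is 0.87 to 1.06 standard errors in (a) and 0.51 to 0.66 in (b). Two-sided rejection rates under no effect are 14–19% and 8–10%, mostly in the direction of apparent harm. Clustering would lower these ratios.

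**Other readings, same 10 points:**
- Late qualifiers have no pre-start score: +0.05 to +0.39 if they qualify on the analysed follow-up, about 0 otherwise.
- The post-start qualifying score is itself the analysed baseline: 0 if no pre-start score exists, down to −0.16 if an earlier score was 9 or less.
- All qualifying scores are separate from the analysed ones: 0 if correlation does not weaken with time. Under one assumed decay pattern it is +0.41 to +0.62.

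**Check by a different model.** A normal model (means 5 to 7, SD 5 to 6, ρ 0.5 to 0.7), in which late entrants qualify on a later score whatever their pre-start score, gives 0.5 to 1.8 points at a 25-point excess, again against the intervention. With all entry dated pre-start, the simulated difference returns to 0.00–0.03 and type I error to 0.048–0.053.

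**A1C.** Assume A1C SD 1.2 to 1.8, correlation with PHQ-9 of 0.1 to 0.3 at the same time and half that when lagged, selection intensity 1.242, and a 50-point excess of late entrants. This takes the 80 to be pooled, which the SAP implies but does not state.
- Low: 0.375 × 0.5 × 0.05 × 1.242 × 1.2 = 0.014.
- High (qualifying at follow-up, factor 2): 0.375 × 0.5 × 2 × 0.15 × 1.242 × 1.8 = 0.126.

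So about 0.01 to 0.13 percentage points.

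**The case against.** The best case against rests on four arguments.

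**The baseline is probably pre-start.** Table 2 labels the value as pre-intervention, defines that period for process measures as the 12 months before, and Data Collection uses the label the same way. This stands. A reader might infer that Table 2 deliberately admits a baseline from after the start. The text does not say so, and that reading would in any case give a shift of about 0 to −0.16. What remains is a need for explicit wording.

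**The relevant patients may have no pre-start score.** People found only by new screening may never have been scored before, and then the shift is at most about 0.4. This also stands as a possibility. The documents do not say which case applies, so the larger figures are conditional.

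**The DD route may drop out.** Under Table 2, distress-only entrants are not in the PHQ-9 analysis. A reader might infer a large bias from them; Table 2 as written does not support it. That control clinics did not take up distress screening later is likewise inferred. The undated PHQ-9 route remains either way.

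**This is a small pilot.** PHQ-9 is a secondary hypothesis in a two-versus-two design that protocol section 4 calls unsuited to conclusive claims. True, but the SAP still tests the outcome at two-sided 0.05, and the repair needs no new data.

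**Conclusion.** The concern holds as a weakness in the entry rule, not as a demonstrated bias. The rule lets screening that differs by arm determine who is analysed for PHQ-9, and the model cannot correct for it. The shift is about 0.4 to 1.4 points per 10-point excess of late qualifiers who have a pre-start score of 9 or less. It is smaller, zero or slightly negative under other readings. The inputs and the 10-point excess are assumptions; the true imbalance is unknown.

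A reader might infer that the plan risks a spurious benefit. The main scenarios point the other way: they would hide one. A reader might also infer that A1C is seriously affected, or that its bias has a firm ceiling. Neither is supported. Entry is not on A1C and 62.5% of charts are unselected on symptoms, so about 0.01 to 0.13 is a plausible range, not a bound.

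Separately, since 37.5% of charts come from a symptomatic list, the protocol's generalisability statement can apply only to the random 50. This should be fixed; confidence is medium.

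**What to change.** 1. Limit the PHQ-9 arm comparison, in all four clinics, to patients with PHQ-9 above 9 recorded before the clinic pair's start date. Stay within the stated data window ("We evaluated quantitative data 12 months before the first facilitation visit (pre-intervention) to six-months after the last facilitation visit (post-intervention") and use the pairing already in place ("adjusting data collection for IC2 and its matched control clinic 2 (CC2"). State one pre-start baseline definition, and reconcile Data Collection with Table 2 on who is analysed.
2. Report entry counts by route, date (before or after the start) and arm. Describe distress-only entrants separately.
3. Report A1C on the random 50 per clinic alongside the pooled 80, counting duplicates once. Restrict the generalisability statement in protocol section 5.i to the random 50.

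**Cost.** SAP wording and reclassification of charts already drawn. If the symptomatic list was sampled at random, its pre-start qualifiers remain a random subset, so no re-draw is needed. If a fraction m of one arm drops out, the standard error grows by √((1 + 1/(1−m))/2): 1.03 at 10%, 1.06 at 20%, 1.22 at 50%. At 10%, root mean squared error falls from 1.15–1.93 to 0.85–1.26 in case (a) and from 0.94–1.51 to the same range in case (b). Where there was no bias, about 3% of precision is lost. A practice just over the 100-patient minimum would have about 10, 20 or 30 depressed patients at an assumed 10%, 20% or 30% prevalence, so fewer than 30 may qualify.

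For A1C, the random-50 standard error is √(80/50) = 1.26 times larger, so that analysis is added, not substituted. The fix does not address whether follow-up PHQ-9 scores are recorded more often in one arm.
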